14.5 Secondary outcomes

The component parts of the primary outcome – fever resolution, and no antibiotic prescription by 16 days post-randomisation – will be analysed using the DURATIONS method in the first instance. As a secondary analysis they will also be analysed as binary outcomes using logistic regression models and adjusting for duration group and minimisation variables: age and sex. The 10-day cefalexin treatment arm will be treated as the control group in these analyses. Microbiological cure (urine sterilisation) at day 16, and UTI recurrence (including relapse and reinfection) at 30 days will be analysed using the DURATIONS method. Quality of life (CHU9D) will be summarised using means and standard deviations at each timepoint. Longitudinal plots of the mean scores over time by treatment group will be produced for visual inspection. Difference in group means and associated confidence intervals at 16- and 30- days post randomisation will be estimated using a repeated measures method.

The number and percentage of participants experiencing any antibiotic-related adverse events will be presented by treatment group alongside the number of events reported. A p-value will be reported from a chi-squared test.

For antimicrobial resistance outcomes, we will describe the overall rates of antibiotic resistance of urinary pathogens within pre- and post-treatment urine samples. We will also describe regional rates of antibiotic resistance, and determine whether any differences that are found correlate with local antibiotic usage data (AMR local indicators) produced by the UK Health Security Agency (UKHSA) and published by the Office for Health Improvement & Disparities: Fingertips Public Health Data (43).

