2.2 Main trial objectives

2.2.1 Clinical objectives

- 1. To determine the optimal (shortest effective) cefalexin duration for the treatment of febrile UTIs in children, to achieve clinical cure (**primary objective**).
- 2. To assess the impact of cefalexin treatment duration on UTI recurrence (relapse or reinfection) up to 30 days post-randomisation.
- 3. To assess the impact of cefalexin treatment duration on microbiological cure and antimicrobial resistance.
- 4. To assess the impact of cefalexin treatment duration on antibiotic-associated adverse events, including diarrhoea, rashes, and candida infections.
- 5. To assess patient adherence to the trial drug across the treatment duration arms.
- 6. Differences in quality of life (using the Child Health Utility instrument CHU9D) between the different treatment duration arms.

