8.2 Secondary outcomes

8.2.1 Clinical

UTI recurrence

- Relapse (recurrent infection with the original bacterial strain) up to final follow-up, 30 days post-randomisation.
- Reinfection (recurrent infection with a different bacterial strain) up to final follow-up, 30 days post-randomisation.

Individual components of the primary outcome

- Fever resolution at the primary outcome assessment visit.
- No additional systemic antibiotic prescription by the primary outcome assessment visit

Microbiological cure

• Urine sterilisation at the primary outcome assessment visit.

Antibiotic-associated adverse events

• Antibiotic-associated adverse events, including diarrhoea, rash, and candida infections.

Adherence to trial drug

• No more than one missed dose from the allocated full course, as logged on the medicine tracker page of the CURLY app and no additional dose(s) beyond the assigned treatment duration.

Antimicrobial resistance & ESBL rates

- Overall rates of antibiotic resistance of urinary pathogens within pre- and post-treatment urine samples.
- Regional rates of antibiotic resistance.
- Identification of ESBL-producing organisms within post-treatment urine samples.

Quality of life – CHU9D

• Differences in quality of life (using the Child Health Utility instrument CHU9D) between the different treatment duration arms (40).

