9.2.7 Testing for antimicrobial resistance and ESBL rates

We expect the majority of participants will be microbiologically cured after treatment (i.e. their posttreatment urine cultures will be negative). However, some participants may have significant posttreatment bacteriuria; possible reasons are persistence or recurrence of the original infection, or secondary infection with a different (and likely more antibiotic-resistant) bacterium. Different treatment durations may be associated with different risks of, and reasons for, failure to achieve microbiological cure.

We will investigate this first by comparing the species and antibiotic sensitivities of bacterial isolates from pre- and post-treatment urine samples. Species identification and antibiotic susceptibility testing will be performed by the local laboratories, following their routine standard operating procedures. Antibiotic susceptibilities will be reported following the European Committee on Antimicrobial Susceptibility Testing (EUCAST) breakpoint tables

(https://www.eucast.org/clinical_breakpoints; v13.0; date accessed: 03/05/2023).

We expect the great majority of Gram-negative urinary isolates in the study population to be E. coli or Klebsiella species. Cefalexin resistance in these bacteria is mainly conferred by production of ESBL. Primary outcome visit (post-treatment) isolates of Gram-negative bacteria will undergo testing for ESBL-production. All Enterobacterales isolated will be speciated using matrix-assisted laser desorption ionization time-of-flight mass spectrometry (MALDI-TOF MS) and screened phenotypically for ESBL production by subculture onto a selective indicator medium (such as CHROMagar™ ESBL, or similar). Isolates of phenotypic ESBL producers will then be stored on nutrient agar slopes and transferred to the UoB Microbiology laboratory for future studies of ESBL gene subtype.

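### Resistance is planned only as overall and regional rates, so the resistance half of objective 3 has no stated comparison by randomised duration

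*Protocol*

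**What the plan says.** Protocol section 2.2.1 sets objective 3: "To assess the impact of cefalexin treatment duration on microbiological cure and antimicrobial resistance". Section 1.2.2 faults two-duration trials for saying nothing about resistance at the durations in between, and says that the design will yield duration-response curves for primary and secondary outcomes. Resistance is one of the listed secondary outcomes.

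Section 8.2.1 defines the resistance outcomes as "Overall rates of antibiotic resistance of urinary pathogens within pre- and post-treatment urine samples", regional rates, and "Identification of ESBL-producing organisms within post-treatment urine samples". Section 14.5 then gives the analysis: "we will describe the overall rates of antibiotic resistance of urinary pathogens within pre- and post-treatment urine samples". It continues: "We will also describe regional rates of antibiotic resistance, and determine whether any differences that are found correlate with local antibiotic usage data". Neither section mentions arm or duration for resistance, and section 14.5 does not mention ESBL.

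Section 9.2.7 describes the laboratory work. It says "We expect the majority of participants will be microbiologically cured after treatment" and that "Different treatment durations may be associated with different risks of, and reasons for, failure to achieve microbiological cure". It will look into this first by "comparing the species and antibiotic sensitivities of bacterial isolates from pre- and post-treatment urine samples". ESBL testing is planned for Gram-negative isolates from the day-16 visit.

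**The concern.** Lower selection pressure for resistant organisms is one of the main reasons given for shortening treatment (section 1.2.1). The trial randomises duration, so it can compare resistance between durations without confounding. The analysis that is written down does not use the randomisation: it pools the five arms before and after treatment, and it relates regional differences to outside usage data, which is an ecological correlation.

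A second risk follows from the obvious repair. If the stated rates were just tabulated by arm, with cultured organisms as the denominator, the comparison would condition on still having bacteria in the urine. That is an event after randomisation which may itself depend on duration. The overall before-and-after contrast has a related weakness, because nearly all children contribute an organism before treatment and only a selected minority do so afterwards.

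**Working it through.** **1. Objective against analysis.** These are the outcomes in protocol section 14.5:

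- Fever resolution and no further antibiotic: DURATIONS method, then logistic regression with the 10-day arm as control.
- Urine sterilisation and recurrence: DURATIONS method.
- Quality of life: differences between group means.
- Antibiotic-related adverse events: by treatment group, with a chi-squared test.
- Resistance: overall and regional description.
- ESBL: nothing stated.

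Resistance is thus the exception in a section that otherwise names an analysis by duration or by group. Other parts of the protocol do not fill the gap. Section 15.1 assigns resistance costs from antibiotic use, not from observed resistance. The work in section 24.1.2 on duration and resistance is optional, at selected sites, separately funded and separately reported.

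**2. Numbers available.** The protocol gives no post-treatment resistance rate. Its sample size reproduces: 500 / (0.88 × 0.90 × 0.90) = 701.5, against 705 stated. Forward, 705 × 0.88 × 0.90 × 0.90 = 502.5, or about 100 per arm in the microbiological-confirmed population.

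**3. Effect of the denominator (all rates assumed).** Let r be the share of children with a resistant organism at day 16 and s the share with a susceptible one. Resistance per isolate is r / (r + s), and per child it is r.

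| Assumed r, both arms | Assumed s, 3 d v 10 d | Per isolate, 3 d v 10 d | Per child |
|---|---|---|---|
| 2% | 15% v 5% | 0.02/0.17 = 11.8% v 0.02/0.07 = 28.6% | 2% v 2% |
| 2% | 10% v 4% | 0.02/0.12 = 16.7% v 0.02/0.06 = 33.3% | 2% v 2% |
| 5% | 25% v 5% | 5/30 = 16.7% v 5/10 = 50% | 5% v 5% |

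In the first row the ratio per isolate is 28.6 / 11.8 = 2.4, with no difference per child. The error can also run the other way: 6 resistant of 30 isolates against 2 of 10 is 20% in both arms, yet with 100 children per arm it is 6% against 2% per child. If s does not vary with duration, the distortion disappears.

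**4. What a per-child endpoint could show.** At 2%, 500 × 0.02 = 10 events, about 2 per arm. Power for two arms of n = 100, with an assumed two-sided alpha of 0.05, is Φ{[|p1 − p2| − 1.96√(2p̄(1 − p̄)/n)] / √[(p1(1 − p1) + p2(1 − p2))/n]}, where p̄ is the mean of p1 and p2.

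- 5% v 10%: (0.05 − 1.96 × 0.03725) / 0.03708 = −0.62, so power is 27%.
- 5% v 15%: (0.10 − 1.96 × 0.04243) / 0.04183 = 0.40, so power is 66%.

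A simulated linear trend over all five arms gives 31% and 74% for the same end points.

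**The case against.** The protocol calls section 14 a brief overview, leaves detail to a SAP, and says that all participants are analysed by randomised duration. Section 1.2.2 promises curves for secondary outcomes in general. On that reading, a tabulation of resistance by arm is implied, and denominators and ESBL tables are ordinary SAP content. This has some force: the SAP may well add the comparison. But the sentence on randomised duration is a rule about how to assign participants to groups and defines no resistance endpoint, and the general promise in section 1.2.2 conflicts with section 14.5, which names a different, pooled analysis for this outcome alone. A mismatch between an objective and its stated analysis is not the same as a missing detail.

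It is also fair to say that with perhaps ten events, description is all that the data can bear. That argues against a fractional-polynomial curve, but not against description by arm.

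The per-child endpoint has limits of its own, and these stand. Restricting it to children with a day-16 sample again conditions on something after randomisation, and section 9.6 expects some samples to be missing. Day 16 falls 16 − 3 = 13 days after a 3-day course but 16 − 10 = 6 days after a 10-day course, so a difference by arm mixes duration with time off drug. The baseline culture definition allows a second organism, and a day-16 organism may be a different strain, so resistance in a child with a susceptible baseline pathogen is newly detected but not proven newly acquired.

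**Conclusion.** The point holds in limited form: the resistance outcomes, ESBL included, have no stated analysis by randomised duration, although objective 3 and section 1.2.2 call for one. It does not affect the primary analysis. It is worth correcting because resistance is a main rationale for the trial and the correction is nearly free.

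Three stronger readings are tempting and are not supported by the documents:

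- A reader might infer that objective 3 as a whole goes unanswered. It does not: urine sterilisation is modelled against duration.
- A reader might infer that the protocol commits to a biased comparison of isolates between arms. It states no denominator. That isolates are meant is an inference from the wording of sections 8.2.1 and 14.5 and from the isolate comparison in section 9.2.7, and section 14.5 plans no split by arm.
- A reader might take the 2.4-fold contrast as an expected result. It is an illustration on assumed rates, and it needs susceptible bacteriuria to fall with longer treatment. It shows only that the choice of denominator can create or hide a difference.

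**What to change.** In section 14.5, or in the SAP with section 8.2.1 brought into line, add one endpoint per child in the microbiological-confirmed population: a cefalexin-resistant or ESBL-producing uropathogen in day-16 urine, yes or no, among children with a day-16 sample. State which growth threshold counts; section 9.2.6 already provides one. Report it by randomised arm with confidence intervals and, if events allow, a simple logistic trend on duration. Report the number of missing day-16 samples by arm. Keep the isolate and regional rates, labelled as description.

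Say in the text that this is estimation with low power and not a confirmatory test, that day-16 resistance is newly detected and not proven newly acquired, and that time off drug at day 16 differs between arms.

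The cost is wording and one further table. Day-16 culture, sensitivity and ESBL testing are already planned in sections 9.1.5 and 9.2.7, so no new samples, visits or participants are needed.

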14.6 Subgroup analyses

Subgroup analyses of the minimisation variables: age (3 months - <3 years, 3 – 11 years) and sex, and also *E. coli* versus non-*E. coli* UTIs, will be assessed visually by producing curves for each of the strata

and assessing the optimal duration for each strata. Due to the use of fractional polynomials, at present it is not possible to include an interaction term, though we will continue to monitor any future work that may help us run these analyses. Construction of the duration-response curve by strata will be underpowered to produce accurate curves and so will be hypothesis generating only.

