6.4.1 Randomisation method

Participants will be randomised at the level of the individual in a 1:1:1:1:1 ratio to one of five cefalexin course durations (3, 5, 6, 8 or 10 days).

A minimisation algorithm will be used within the randomisation system to ensure balance in the intervention allocations over the following variables:

- Age (3 months <3 years vs 3-11 years)
- Sex (male vs female)
- Participating centre

To avoid the possibility of the intervention allocation becoming predictable, a random element will be included in the algorithm. Full details of the randomisation specification will be stored in a confidential document at BCTU.

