14.4 Primary outcome

The primary outcome is clinical UTI cure rate, defined as patients in whom there is (i) fever resolution and (ii) no additional systemic antibiotic prescription by 16 days post-randomisation. A duration-response curve will be fitted using a fixed-2 fractional-polynomial model. This curve will then be analysed to obtain the optimal number of days (D*), such that the UTI cure rate preserves at least 90% of the efficacy provided by the maximum length (10 day) course of antibiotics. A confidence interval will be constructed around D* using bootstrapping methods and the smallest

duration that is greater than the upper end of the confidence interval, will be the recommended duration required (30). Figure 3 provides an example of a hypothetical curve and how the optimal duration will be calculated. This analysis will be performed for both the primary and ITT analysis cohorts as described in Sections 14.2 and 14.3.

Figure 3: Hypothetical duration-response curve

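### Section 14.6 wrongly says fractional polynomials rule out an interaction term, and so compares subgroup curves by eye with no stated test or interval

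*Protocol*

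**What the plan says.** - **Primary model (protocol 14.4).** "A duration-response curve will be fitted using a fixed-2 fractional-polynomial model". D* is then the duration at which the cure rate keeps at least 90% of the 10-day efficacy, with a bootstrap confidence interval. The section neither lists nor excludes covariates.
- **Subgroups (14.6).** Age, sex and *E. coli* versus other organisms "will be assessed visually by producing curves for each of the strata", with an optimal duration assessed in each stratum. The reason given for having no interaction test is "Due to the use of fractional polynomials, at present it is not possible to include an interaction term". The authors will watch for future methods, and they add a caveat: "Construction of the duration-response curve by strata will be underpowered to produce accurate curves and so will be hypothesis generating only".
- **Minimisation (6.4.1).** Three factors are balanced: age group, sex and "Participating centre".
- **Secondary logistic models (14.5).** The two components of the primary outcome are also "analysed as binary outcomes using logistic regression models and adjusting for duration group and minimisation variables: age and sex". Centre is not named, and no reason is given.

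**The concern.** The sentence in 14.6 is a positive statement about what the model can do, and it is the stated ground for the visual method. It is not a detail left for the SAP to settle, because an SAP written to agree with the protocol would inherit both the wrong reason and the method.

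What is at stake is how between-stratum differences will be read. The plan will produce a D* for each stratum of age, sex and organism but gives no measure of whether two such values differ by more than chance. Three of the four gaps between neighbouring arms (3 to 5, 6 to 8 and 8 to 10 days) are exactly 2 days, so a 2-day difference in estimated D* would look like a difference of one arm.

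The centre point is smaller. One of the two outcomes in the 14.5 models is further antibiotic prescription. Section 7.5 leaves that to the clinician's discretion, and section 6.5 makes the trial open label. Practice could plausibly differ by centre, although the documents give no figure for it.

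**Working it through.** **1. Size of the analysis set.** Section 14.1 assumes 12% without proven UTI, 10% of proven UTIs resistant and 10% lost to follow-up.

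- 500 / (0.88 × 0.90 × 0.90) = 500 / 0.7128 = 702, against the stated 705.
- 705 × 0.7128 = 502.5, so 500 in all and 100 per arm is a fair basis. An even two-way split leaves 50 per arm in each stratum.

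**2. The algebra.** Let f1(d) and f2(d) be the two transformed durations for given powers, and g = 0 or 1 the stratum.

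- Common shape: logit p = b0 + b1·f1 + b2·f2 + c0·g (4 coefficients).
- With interaction: add c1·g·f1 + c2·g·f2 (6 coefficients).

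The second model is linear in its coefficients. With common powers it is also the same fit as two separate stratum curves with 3 coefficients each (2 × 3 = 6). So fitting a curve per stratum, as 14.6 plans, already fits the interaction model; what is missing is the comparison with the 4-coefficient model. Five arms by two strata give 10 cells, enough for 6 coefficients.

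**3. Does it work at N = 500?** Trials were simulated with 100 per arm at 3, 5, 6, 8 and 10 days. The protocol gives no cure rates, so these are assumptions:

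- No interaction: 75% at 3 days rising to 90% at 10 days in both strata.
- Large interaction: 55% to 90% in one stratum, 88% to 90% in the other.

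| Setting | Converged | Type I error (nominal 5%) | Power |
|---|---|---|---|
| Five fixed power pairs, stratum share 50% or 30%, 500 runs each | 500/500 in every setting | 4.2% to 7.6% | 55% to 66% |
| Best of 36 power pairs, one further binary covariate in the model | 200/200 | 3.0% | not run |

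The fixed-power interaction model was full rank (6 of 6 columns) throughout. The ten fixed-power type I errors were 5.2, 7.2, 4.6, 7.0, 7.6, 5.4, 6.6, 5.6, 4.2 and 5.6%. Their mean is 59.0 / 10 = 5.9% over 5,000 runs, with a simulation standard error of √(0.05 × 0.95 / 5000) = 0.3 percentage points. The likelihood-ratio test therefore runs slightly high, which is the reason to prefer a bootstrap reference.

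**4. How noisy is a by-eye comparison?** Two strata were simulated with identical true curves, split 50/50 or 70/30 per arm. Estimated D* differed by 2 days or more in 10% to 20% of trials for a curve rising from 80% to 92% with an early plateau, and in 42% to 49% for a straight line from 78% to 92%. The ranges cover different plateau shapes and choices of powers.

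**5. The product test is not a test of equal D\*.** D* depends on 90% of the 10-day rate, so equal logit slopes do not imply equal D*.

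- 10-day rate 0.90: threshold 0.81; allowed logit drop ln(0.90/0.10) − ln(0.81/0.19) = 2.197 − 1.450 = 0.747.
- 10-day rate 0.92: threshold 0.828; allowed logit drop ln(0.92/0.08) − ln(0.828/0.172) = 2.442 − 1.572 = 0.870.

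The same logit shape thus reaches the threshold at different durations. An interval for the difference in D* is needed as well as the test.

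**The case against.** The best defence is that 14.6 is already modest. It calls the stratum curves underpowered and exploratory, and descriptive curves under that caveat are defensible. The noise in step 4 illustrates the caveat; it is not caused by the wrong sentence, and product terms would not make a stratum D* less variable. Power of 55% to 66% for a large interaction supports the caution. The words at present may also mean only that no ready-made DURATIONS procedure handles interactions. All of this stands, and it limits the severity. It does not make the stated reason true, and it gives the reader no measure of the difference between strata.

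Some stronger readings are tempting and are not supported:

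- **That the primary curve omits the minimisation factors.** Section 14.4 is only silent on covariates, and section 14 calls itself a brief overview with a separate SAP to follow. Section 14.5 does adjust its logistic models for age and sex.
- **That missing covariates and the missing interaction share one wrong premise.** The protocol gives the fractional-polynomial reason for the interaction term alone.
- **That each stratum's D\* is read off by eye.** Section 14.4 defines D* by a numerical rule with a bootstrap interval, and nothing in 14.6 suspends that. The by-eye element is the comparison between strata.
- **That leaving out centre makes standard errors too wide.** In logistic regression, adjusting for a prognostic factor generally does not shrink the standard error of the conditional log odds ratio. The case for centre is that the analysis should follow the factors used in allocation.

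**Conclusion.** The statement that an interaction term cannot be included is wrong as a statement about the model. It rests on nothing more than linearity once the powers are set, and the simulations bear it out with both fixed and data-selected powers. The visual comparison therefore lacks its stated justification, and the section names no test or interval for a difference between strata.

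The error and power rates depend on the assumed cure curves. The noise figures in step 4 do so strongly, and should be read as a range (10% to 49%) rather than as a prediction.

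The severity is minor. No primary estimate, sample size or decision rule changes, and the subgroup results are already labelled exploratory. The absence of centre from the 14.5 models is a secondary point within an analysis that is itself secondary.

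**What to change.** **Section 14.6.** Delete the impossibility sentence and keep the low-power caveat. Pre-specify, as exploratory:

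1. powers fixed from the overall fit, then the stratum main effect and two stratum-by-term products, tested on 2 degrees of freedom, preferably against a bootstrap reference generated under the no-interaction model;
2. a bootstrap interval for the between-stratum difference in D*, with a stated rule for replicates in which D* falls at the edge of the 3 to 10 day range.

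The stratum curves can still be shown beside these results.

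**Section 14.5.** Add participating centre to the logistic models, for example as a random intercept, or say why it is left out.

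**Cost.** A protocol wording change, matching SAP text and modest programming. All the data are already due to be collected. The limit to state openly is low power: a non-significant interaction test will not show that the strata share one optimal duration.
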